#### **9.6.12. Pregnancy Screen**

All WOCBP will have a serum pregnancy test at Screening and at the ETV visit, if applicable.

Urine pregnancy tests will be performed pre-dose for WOCBP at all other specified subsequent visits. Urine pregnancy tests may be performed in the clinic using a human chorionic gonadotropin (hCG) pregnancy test.

If a urine pregnancy test is positive, it must be confirmed by a serum pregnancy test.

#### **9.6.13. Alcohol Breath Test**

An alcohol breath test will be performed at screening and other times according to the study schedule. A negative result is required for entry and continuation in the study.

#### **9.6.14. CT or MRI Imaging**

Part B only: Assess the radiological validation of the herniated disc (MRI or CT Scan within the last 6 months). If an MRI or CT scan does not exist, it is important to order this

---

investigation for review prior to administration of the IMP to fulfil necessary validation of entry criteria. MRI is the preferred imaging report unless not appropriate due to metal implants.

#### **9.6.15. Pain assessment (VAS), Patient General Impression of Change (PGIC) and Bang Binding Index Assessment (Part B only)**

Pain Assessments will be completed using a Visual Analogue Scale (VAS). VAS scores will be collected at the timepoints in Schedule 2.

The Patient General Impression of Change will be collected at the timepoints in Schedule 2. Bang Binding Index Assessment will be collected at the timepoints in Schedule 2

#### **9.6.16. PK and PD Sampling**

PK and PD sample analysis will be performed using validated or fit-for-purpose methods as outlined in the Laboratory Manual.

The Sponsor will supply complete written instructions for handling, processing, storage, and shipping of samples prior to study initiation.

Pharmacokinetic and Pharmodynamic samples will be taken at the timepoints in schedule 1 and 2. The samples will be sent to a certified Central Laboratory for analysis.

Blood samples for plasma PK and PD will be obtained at the following time points:

Part A: Predose, 5, 15, 30 minutes, 1, 2, 4 and 6 hours post IV injection.

Part B: Predose, 5, 10, 20, 30, 45 minutes, 1 and 6 hours from the start of the IV infusion.

Collecting 4 mLs in a K2EDTA tube for the PK sample and 8mLs for the PD Samples.

The PK Population will include all randomized participants who received LAT8881, with exploitable PK data and without relevant deviations interfering with the PK evaluations. The PK Population will be used for the summaries and analyses of all PK data.

#### **9.6.17. Mechanical QST assessment using Von Frey Aesthesiometer (Part B only)**

Evaluate mechanical Quantitative Sensory Test (QST) assessment to detect sensory changes to light touch on affected and non-affected dermatomes using von Frey Aesthesiometer on six occasions, once prior to dosing and once 2 hours and 4 hours post dosing. This will occur for each dosing occasion.

QST measurements will be completed by staff trained on performance of this test.

## 10. INVESTIGATIONAL PRODUCT (IP) DISPENSING AND ACCOUNTABILITY

LAT8881 will be stored and handled by the pharmacist(s) according to study Pharmacy Manual (provided by the Sponsor or its designee), the pharmacy's standard operating procedures, applicable laws, and regulatory requirements.

The investigator or designee must confirm appropriate temperature conditions have been maintained during transit for all investigational product received and any discrepancies are reported and resolved before use of the investigational product.

Only participants enrolled in the study may receive investigational product and only authorized site staff may supply or administer investigational product. All investigational product must be stored in a secure, environmentally controlled, and monitored (manual or automated) area in accordance with the labeled storage conditions with access limited to the investigator and authorized site staff. The investigator is responsible for investigational product accountability, reconciliation, and record maintenance (i.e., receipt, reconciliation, and final disposition records). Further guidance and information for the final disposition of unused investigational products are provided in the Study Pharmacy Manual.

## 11. Administration

### Part A:

LAT8881 is administered at a dose of 0.8 mg/kg, 1.2 mg/kg and 1.8 mg/kg via an infusion pump at a constant rate over 5 minutes. The LAT8881 formulation will be presented in a polypropylene luer lock syringe containing the following:

- LAT8881 10 mg/ml (active)
- DSPE-PEG2000 20 mg/ml (Buffer)
- Mannitol 47 mg/ml (Tonicity)
- Sodium Hydroxide 0.33 mg/ml (Buffer)

### Part B:

LAT8881 is administered at a dose of 1.8 mg/kg via an infusion pump at a constant rate over 10 minutes.

The placebo formulation will be presented as above but without the LAT8881 active.

To minimise potential local infusion site irritation or reaction, the LAT8881 infusion will be administered in line with a continuous infusion of 5% Dextrose Solution (50 g of glucose in water for injection, or equivalent). The dextrose solution infusion will commence approximately 30 minutes pre-dose and continue until the participant ceases fasting.

The rate of dextrose solution will be 80mls/hr. The IV dosing/ Normal Saline infusion cannula will be inserted into the opposite arm to the PK sampling IV Cannula to avoid any dilution of the PK samples.

Further details on the administration process can be found in the Pharmacy Manual.

## 12. Investigational Product Compliance

The participant will receive investigational product directly from the investigator or designee, under medical supervision. The date and time of each dose administered in the clinic will be recorded in the source documents. The dose of investigational product and study participant identification will be confirmed at the time of dosing by a member of the study site staff other than the person administering the investigational product.

## 13. COVID-19 CONSIDERATIONS AND CONTINGENCY PLANNING

Information regarding COVID-19 risk and considerations is included in the PICF, to ensure that study participants are cogniscent of the potential impact on the study and schedule. All participating sites must confirm that they are compliant with local infection control policies related to COVID-19.

## 14. BLINDING, PACKAGING AND SHIPPING

The IP for all sites will be manufactured and packaged by a contracted certified pharmacy. Treatment packs will be shipped to study sites on completion of a remote Site Initiation Visit (SIV).

IP will be labelled with:

- Study Protocol Number
- Randomisation number and participant details
- Instructions for Storage
- Instructions for Use

All participant-facing study personnel, including the CPI, Site PIs, and site study teams (including central coordinating team), will be blinded to treatment allocation until data collection is completed for all participants and the database is locked.

To maintain blinding for participant-facing study personnel, the study drug and placebo will be presented in identical sized syringes with clear liquid, and the packaging will also be identical for both study drug and placebo. Treatment allocation will not be discernable by differences in appearance. The study interventions do not differ across the treatment groups, and study SOPs guiding data collection, particularly participant-reported data, assist with reducing risk of inadvertent unblinding and discourage speculation regarding treatment allocation.

### 14.1. Method for assigning subject study number

At screening, each subject will, in chronological order, be allocated a unique Screening Number (Subject ID).

At randomisation on Day 1, the subject will be manually assigned a unique Randomisation Number, which will be allocated in ascending order according to their chronological order of inclusion in the study.

Confirmation of the randomisation number allocated to each subject will be documented in the drug accountability records and recorded in the CRF.

For Part A, randomisation will be employed is to identify subjects have placebo on the three treatment days. For Part B, randomisation is to identify the treatment sequence.

The Subject ID number will be used to identify the subject throughout the study period and on all study-related documentation.

## 15. UNBLINDING

Blinding of treatment assignment is critical to the integrity of this clinical study. In the event of a medical emergency or pregnancy in an individual participant in which knowledge of the IP is critical to the participant's management, the blind for that participant may be broken. The participant's safety takes priority over any other considerations in determining if a treatment assignment should be unblinded.

If a decision is made to unblind a participant, the Site PI will access to an envelope containing the unblinding information. For any participant unblinded and/or withdrawn from the study, the appropriateness and requirements for further monitoring blood tests and urine tests as per the Study Schedule following emergency unblinding will be decided by the Site PI. This will depend on the clinical circumstances surrounding unblinding.

Any request to unblind a participant for non-emergency purposes should be discussed with the Sponsor.

## 16. SAFETY ASSESSMENTS

Safety bloods will be performed at each study timepoint, and any early termination visit. Participants will undergo physical examination at study visits, as described in the Schedule of Events. AEs will be identified via:

- Participant report
- Observations (e.g. vital signs, physical examination)
- UA via dipstick
- Safety blood tests (and MSU, if applicable)
- Fasting pre-dose and in the immediate post dose period

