Secondary endpoints	
Part A:
 
 
• Pharmacokinetic profile
 
 
Part B:
 
 
• Comparison of radicular “pain now” scores as peak change from baseline and area under the curve comparing the two arms over the full six hours
 
• Comparison of Patients general impression of change between dosing arms
 
• Adverse event rates in each dosing arm
 

Exploratory endpoints	
Part A:
 
 
• Pharmacodynamic assay and/or biomarkers of LAT8881 activity.
 
 
Part B:
 
 
• Mechanical QST assessment using Von Frey Aesthesiometer
 
• Evaluate the effect of Intravenous LAT8881, compared with placebo, on VAS radicular pain scores during straight-leg raise nerve stretch
 
• Bang Binding Index assessment, whereby participant will be asked to record which dosing occasion they believe they got the active IP.
 
• Pharmacodynamic assay and/or biomarkers of LAT8881 activity.
 

Study Design	
Part A:
 
This is a double-blind, randomized, placebo-controlled, single ascending dose study within 8 healthy volunteers of intravenous administration of LAT8881 over 5 minutes.
 
Part A of the Study will enrol 8 participants, each participant has three treatment days, 1 infusion per dosing day on days 1, 4 and 7 as well as two short visits for safety blood sampling on Day 3 and 6. The 8 subjects will be split into two groups of 4 subjects each (3 IMP and 1 placebo), with the two groups dosed a few days apart.
 
Participants arrive on the morning of treatment day, receive a single infusion, leave that afternoon (no overnight stay). Participants will be dosed at staggered intervals as determined by PI. .
 
Treatments are on Days 1 (0.8 mg/kg), Day 4 (1.2 mg/kg) and Day 7 (1.8 mg/kg) or placebo to allow sufficient washout and consideration of any safety observed following each dosing day. Day 3 and 6 safety blood results must be review prior dosing on the following day.
 
Participants will fast for 8 hours pre-dose and 4 hours post dose for each dosing occasion.

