## 3. SCHEDULE 1 OF OBSERVATIONS AND PROCEDURES PART A

Procedure	Day -30 to -2	Day 1/Day 4/Day 7 (hours)												Day 3/ 6	Day 14/ ETV
	Screening	Pre- Dose	Dose	5 min	0.25	0.5	1	1.5	2	2.5	3	4	6 Discharge	Day prior dosing 	+/- 2 day
Informed consent	x														
Medical history	x	x													
Inclusion/exclusion criteria	x														
Demography	x														
Physical examination, height, weight	x														
Symptom-directed physical exam		x											x		x
Pregnancy test (WOCBP) 	x	x													x
Urine drug screen, Urinalysis and Alcohol breath test 	x	x													
SARS-CoV-2 Test 															
HIV, Hepatitis B & C screening	x														
Clinical laboratory tests	x												x	x	
12-lead ECG	x	x							x				x		x
Vital signs	x	x			x	x	x	x	x	x	x	x	x		x
Spot pulse oximetry	x	x			x	x	x	x	x	x	x	x	x		x
Randomization		x													
Dose administration 			x												
AE review				x	x	x	x	x	x	x	x	x	x		x
Concomitant medication review	x	x	x	x	x	x	x	x	x	x	x	x	x		x
PK 		x		x	x	x	x	x	x			x	x		
PD 		x		x	x	x	x	x	x			x	x		
Discharge													x		

\*# Participants who withdraw early from the study will be encouraged to return to the clinic for an ETV assessment.

\* Participants may require an unscheduled visit to address safety issues and/or for any additional PK and/or PD sample collection as required.

1 All WOCBP will have a serum pregnancy test at Screening and at the ETV visit, if applicable. Urine pregnancy tests will be performed for WOCBP at all other specified subsequent visits. If a urine pregnancy test is positive, it must be confirmed by a serum pregnancy test.

2. Urine Drug Screen and Alcohol Breath Test will be performed in clinic. A urine dipstick will be completed at all visit. In the event of positive Leukocytes and/or nitrates that urine sample will be sent to the local labortaotry for a microscopic examination.

3. SARS-CoV-2 Test will be taken if clinically indicated and in line with local processes.  
 4. All participants will fast 8 hours prior and 4 hours after the study drug administration  
 5. Samples must be taken with enough time that results are available prior to planned IP dosing on the following morning.  
 6. Pre-dose, 5 ± 1 min, 15 ± 2 min, 30 ± 2 min, 60 ± 5 min, 2 h ± 10 min, 4h ± 20 min, 6h ± 30 min post-dose.

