#### Part B:

A Randomized Placebo-controlled Double-blind Cross-over Proof-of-Concept safety and efficacy study of LAT8881 in participants with lumbar radicular pain

At the conclusion of Part A of the study, safety data and PK data will be collated and presented to HREC along with the justification for dose level and dose interval for Part B, noting that a different cohort of subjects will commence Part B.

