### 7.3. Sample Size

No formal statistical sample size estimation has been performed due to the exploratory nature of this study. Rather the sample size is based on clinical and practical considerations:

- Part A follows a dose escalation design where 8 subjects will be dosed on each of three occasions with an increased dose (6 subjects) or placebo (2 subjects). The 8 subjects will be split into a maximum of two groups of 4 subjects each (3 IMP and 1 placebo), with the groups dosed at least a few days apart. The MTD will be the highest dose level at which no more than 1 of 6 subjects on active dose experience a dose-limiting toxicity.
- In Part B of the study, a proof-of-concept, the sample size will be expanded up to n=20 based on the PI's experience from design and management of lumbar radicular pain subjects.

Overall, a total of 8 subjects (healthy volunteers) are planned for Part A of this study, and up to 20 subjects with lumbar radicular pain are planned to be enrolled in Part B.

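### Protocol section 16 calls for safety bloods at every timepoint, but Schedule 1 plans none after 6 h at 1.8 mg/kg in Part A, and on neither text is there a 48 h sample at that dose

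*Protocol*

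**What the plan says.** Section 16 (Safety Assessments) says "Safety bloods will be performed at each study timepoint, and any early termination visit". In Schedule 1 for Part A (protocol section 3), the row "Clinical laboratory tests" is marked at screening, at 6 h on each dosing day, and at Day 3/6. The Day 14/ETV cell is empty. The synopsis describes "two short visits for safety blood sampling on Day 3 and 6", and footnote 5 of the schedule explains their purpose: "Samples must be taken with enough time that results are available prior to planned IP dosing on the following morning". Section 9.6.9 likewise ties those results to dosing occasions 2 and 3. For the follow-up visit or ETV it lists urinalysis, drug screen and pregnancy testing, but no bloods. Footnote 2 covers urine separately: "A urine dipstick will be completed at all visit".

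Part A doses are 0.8 mg/kg on Day 1, 1.2 mg/kg on Day 4 and 1.8 mg/kg on Day 7, with 6 active and 2 placebo participants each time. Part B uses 1.8 mg/kg. Incidence and severity of laboratory abnormalities is one of four Part A primary safety measures. At the end of Part A, "safety data and PK data will be collated and presented to HREC along with the justification for dose level".

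SAP 12.3.2 summarises each parameter by visit and treatment and lists every value with flags. It builds worst-case and maximum-shift results from all post-baseline samples. SAP 3.2.6 assigns Part B records to a treatment by period. SAP 3.2.5 gives no such rule for Part A, so the Day 3/6 results have no stated dose.

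**The concern.** The two protocol texts disagree about whether blood is drawn at the Part A exit visit, and the disagreement falls on the last and highest dose. Days 3 and 6 look back on the first two doses only because they come before the next one. Nothing follows Day 7 except the exit visit, whose laboratory cell is blank. Adverse events, vital signs and ECG, the other three primary safety measures, are all marked at that visit.

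At stake is the laboratory evidence at the dose carried into patients. The highest earlier intravenous dose described in protocol section 5.2 is 400 µg/kg, so 1.8 mg/kg is 1.8/0.4 = 4.5 times that. A reader of a clean laboratory table at 1.8 mg/kg could also take it as resting on the same follow-up as the lower doses.

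**Working it through.** No published figure is in question, so the check is a count, followed by an illustration of size.

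**1. The schedule row.** Schedule 1 for Part A has 15 columns, and the laboratory row has all 15 cells. The ECG, vital signs, AE review, symptom-directed examination and pregnancy rows also have 15 cells and are all marked at Day 14/ETV. A shifted column therefore does not explain the blank.

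**2. Time from dose to later samples**, as (sample day − dose day) × 24 h:
- 0.8 mg/kg: (3 − 1) × 24 = 48 h.
- 1.2 mg/kg: (6 − 4) × 24 = 48 h.
- 1.8 mg/kg: none on the schedule. If section 16 adds Day 14, (14 − 7) × 24 = 168 h, or 120 to 216 h with the ±2 day window.

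**3. Planned post-dose blood samples**, with Day 3/6 assigned to the preceding dose:

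| | Schedule 1 governs | Day 14 bloods added |
|---|---|---|
| 0.8 mg/kg | 6 × 2 = 12 | 12 |
| 1.2 mg/kg | 6 × 2 = 12 | 12 |
| 1.8 mg/kg | 6 × 1 = 6 | 6 × 2 = 12 |
| Pooled placebo (6 person-doses) | 4 + 4 + 2 = 10 | 4 + 4 + 4 = 12 |

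On the schedule this is 2.0, 2.0, 1.0 and 10/6 = 1.67 samples per person-dose. With Day 14 bloods the counts match, but the times do not: 6 h and 48 h at the lower doses against 6 h and about 168 h at 1.8 mg/kg.

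**4. What a missing late sample could hide (assumed, not from the documents).** Suppose a change is absent at 6 h and present at 48 h with chance q per person. The chance that planned labs show at least one case in 6 is 1 − (1 − q)^6:
- q = 10%: 47%.
- q = 20%: 74%.
- q = 30%: 88%.

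These apply to each lower dose. At 1.8 mg/kg on the schedule the chance is 0, which follows directly from the assumption. With a Day 14 draw and a share f still abnormal, the chance is 1 − (1 − qf)^6. At q = 20% that gives 26%, 47% and 74% for f = 0.25, 0.5 and 1.

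**5. Effect on the worst-case tables, Schedule 1 reading.** Let p be the chance that a sample is abnormal and r the correlation between a person's two samples. One sample flags p; two flag p + p(1 − p)(1 − r). The expected gap for 6 people is 6p(1 − p)(1 − r):
- p = 10%: 0.54 participants at r = 0, 0.27 at r = 0.5, 0 at r = 1.
- p = 5%, r = 0: 0.285.
- p = 20%, r = 0: 0.96.

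Against placebo at p = 10%, r = 0, placebo incidence is (4 × 0.19 + 2 × 0.10)/6 = 0.16, so the gap is 6 × 0.06 = 0.36.

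**6. Direction.** SAP 3.2.1 uses one baseline before the first dose, so a change carried over from Day 1 or Day 4 can count at Day 7. At p = 10% and r = 0.5, two samples flag 0.10 + 0.09 × 0.5 = 0.145. One Day 7 sample with a carry-over chance of 5% flags 1 − 0.90 × 0.95 = 0.145, so the gap to 0.8 mg/kg vanishes. A larger carry-over would reverse it.

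**The case against.** The strongest reply is that section 16 already asks for the Day 14 bloods. The exit visit exists to complete the safety assessment (section 9.5), and Schedule 1 is not reliable cell by cell. Its Part A PK row ticks 1.5 h, giving 9 ticks against the 8 times in footnote 6, and it leaves urinalysis blank at Day 14 although section 9.6.9 and footnote 2 place it there. This stands as far as it goes: the documents do not settle which text governs. But section 9.6.9 sides with the schedule on bloods, and a site working from the schedule would skip the draw.

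Second, the 48 h samples were there to release the next dose, and no dose follows Day 7, so the asymmetry has a reason. That also stands. It explains the design without supplying a late sample.

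Third, other safeguards remain. AE review, ECG and vital signs continue to Day 14, and "Participants may require an unscheduled visit to address safety issues". The dose rule does not use the laboratory tables: "The MTD will be the highest dose level at which no more than 1 of 6 subjects on active dose experience a dose-limiting toxicity". Daily intravenous dosing at up to 10 mg/kg for 28 days in two species raised no concern (section 5.2). All of this lowers the weight of the point.

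Fourth, Part A analysis is descriptive, and the by-visit summaries already compare doses at a common 6 h. That is why the SAP part is minor.

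A reader might go further and infer that Part A certainly holds no blood result beyond 6 h at 1.8 mg/kg, so that Part B patients give the first later look. The documents do not support this without condition, because on the section 16 reading Day 14 bloods are planned.

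**Conclusion.** There is a real conflict between section 16 and Schedule 1. On the schedule, 1.8 mg/kg has no planned haematology or chemistry after 6 h, and on either text it has none at 48 h, while each lower dose does. This is a modest safety-monitoring point for the protocol, because it touches a primary endpoint at the carried-forward dose and costs little to put right. It is a minor reporting point for the SAP. Under the assumed 5% to 20% abnormality per sample the tables shift by at most 0.96 of a participant, and carry-over can cancel or reverse that.

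The detection percentages rest on an assumed late-onset change that no document suggests, so they show what the schedule could miss and are not an estimate of risk. Two further inferences are not supported: that the tables flatter 1.8 mg/kg, since the direction is unknown, and that the Part B dose decision is invalid, since that decision rests on dose-limiting toxicities and the full safety and PK package.

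**What to change.** **Protocol.** Tick clinical laboratory tests at Day 14/ETV in Schedule 1 for Part A, add bloods to the follow-up tests in section 9.6.9, and reword section 16 to refer to the scheduled times. The cost is one blood draw at an existing visit. It does not match the 48 h samples; only a short Day 9 visit would, at 8 extra visits, and I would not insist on that.

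**If Part A is complete.** This is likely, since SAP 2.5 reports 14 Part B completers at the interim and Part B follows Part A. Only reporting changes are then left:
- State in the report whether Day 14 labs were taken.
- Add a rule to SAP 12.3.2 assigning Day 3 and Day 6 results to the preceding dose.
- Keep the worst-case and maximum-shift tables for signal detection, with a footnote saying that laboratory follow-up at 1.8 mg/kg was limited to 6 h. If Day 14 labs were taken, the footnote should say instead that there was no 48 h sample.
- Read dose comparisons from the existing by-visit 6 h summaries.

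The cost is one rule and one footnote. The drawback is that the dose comparison then uses fewer samples.
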